#### 11.1.3. Stratification Factor

AML patients will be stratified by previously untreated vs. treated. The reason is that patients in first lapse are likely to have shorter survival and lower remission rate as compared to previously untreated patients.

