#### 11.1.2. Selection Design

Assuming that at least 2 dosing schedules show activity and that their toxicity profile is similar, a selection design will be used to choose the dosing schedule with the better observed 1-year survival rate. If the better dosing schedule has a true 1-year rate of 45% and the worse dosing schedule a true 1-year rate of 30%, the trial has better than 80% probability to choose the correct dosing schedule if 20 patients have been treated with each dosing schedule.

No formal hypothesis testing will be carried out for the 1-year survival rate. Instead, we will estimate the 1-year survival rate for each dosing schedule, along with the 95% confidence interval. Given a total of 20 patients in an arm and assuming a 1-year survival rate of 45%, the half-width of the 95% confidence interval will be 0.22. On the other hand, if assuming a 1-year survival rate of 30%, the half-width of the 95% confidence interval will be 0.20.

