#### 11.3.3. Stratification Factor

AML and MDS patients will be stratified by prior treatment with decitabine (Yes or No). The reason is that patients who have been treated with decitabine may respond differently to sapacitabine than those who have only received azacitidine. 

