#### 11.4. Data Analysis

The intent-to-treat population for Part 1 of the study will include all patients who have received at least one dose of study drug on an assigned dosing schedule. The primary analysis population will consist of patients who underwent randomization. The primary and secondary efficacy endpoints will be analyzed separately within the AML or MDS stratum. Additional patients accrued to a dosing schedule that has produced at least 20% CR/CRi will be analyzed separately. The rate of 1-year survival and that of CR, CRp, PR CRi, or hematological improvement, will be reported with 95% confidence interval. The intent-totreat population for Part 2 of the study will include all patients who have received at least one dose of the study drug. The rate of clinical benefit response (CR, CRp, PR, major HI or SD) and the rate of CR/CRp with be reported with 97.5% confidence interval. The intent-to-treat population for Part 3 and 4 of the study will include all patients who have received at least one dose of study drug on an assigned dosing schedule. The primary analysis population will consist of patients who underwent randomization. Additional patients accrued to a dosing schedule that has produced at least 20% clinical benefit response rate will be analyzed separately. Duration of CR, CRp, PR, CRi, HI, SD and overall survival will be estimated using the method of Kaplan and Meier. Patients who are discontinued from the study for reasons other than progression of disease will be censored at the time of the last response evaluation. The median number of transfusion-free weeks will be calculated for the 8 weeks

immediately prior to the first dose of study drug and while on study. For patients who required at least one transfusion of RBC or platelet within the 8 weeks immediately prior to the first dose of study drug, there will be a calculation of those who have achieved at least a 50% increase in the number of transfusion-free weeks on study over these at baseline, i.e., during the 8 weeks immediately prior to the receiving the first dose of the study drug.

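### The factors used to stratify randomization are not used afterwards: 1-year survival is estimated and schedules are ranked on the pooled arm rate, at a modest cost that a short addition to 11.4 would recover

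*Combined protocol and SAP*

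**What the plan says.** Section 11.1.3 stratifies Part 1 AML randomization by treatment history: "AML patients will be stratified by previously untreated vs. treated". The reason given is that "patients in first lapse are likely to have shorter survival and lower remission rate" than untreated patients. One-year survival is the primary endpoint, so the protocol itself treats this factor as prognostic for the quantity on which schedules are chosen.

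Section 11.3.3 stratifies Parts 3 and 4 by whether the patient had decitabine before. Its stated ground: "patients who have been treated with decitabine may respond differently to sapacitabine than those who have only received azacitidine". It says nothing about survival. Section 6.1 gives Part 1 MDS no stratification factor.

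Section 3.1 refers the reader to Section 11 for the stratification factors and the analysis plan. There, 11.1.2 and 11.3.2 give one 1-year survival rate and one 95% confidence interval per schedule, with no formal test, and state that "a selection design will be used to choose the dosing schedule with the better observed 1-year survival rate". Section 11.4 adds one separation, for Part 1: "The primary and secondary efficacy endpoints will be analyzed separately within the AML or MDS stratum". No result by factor level, no adjusted estimate and no role in selection is given for untreated/treated or for decitabine.

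**The concern.** Stratified randomization removes part of the chance variation between arms, and an analysis that ignores the factor does not credit this. Three things follow.

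- The crude binomial interval is somewhat wider than the design supports.
- Any residual difference in mix between arms of 20 stays in the ranking, which rests on an assumed difference of 15 points.
- The pooled AML rate is an average over whatever mix of untreated and relapsed patients enrolled. It is hard to set beside Parts 2 and 3, which take only AML not yet treated with systemic therapy.

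**Working it through.** **Inputs from the protocol (11.1.2, repeated in 11.3.2).** 20 patients per schedule; true 1-year rates of 45% and 30%; better than 80% probability of choosing correctly; 95% half-widths of 0.22 and 0.20.

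**Assumptions, because the documents give no values.** The survival gap between factor levels is 0 to 30 points, and the better-prognosis level holds 50% to 80% of patients.

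**1. The plan's own figures.** Half-width = 1.96 × √(p(1−p)/20).
- p = 0.45: 1.96 × √(0.2475/20) = 0.218.
- p = 0.30: 1.96 × √(0.21/20) = 0.201.

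Both match. The exact two-arm binomial selection probability is 0.796 with ties lost and 0.836 with ties split; the normal approximation gives 0.839. The stated figure reproduces with ties split.

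**2. Half-width that credits the stratification.** With share f at rate p₁ and 1−f at rate p₂, the variance under proportional balance is [f·p₁(1−p₁) + (1−f)·p₂(1−p₂)]/20. For p = 0.30, f = 0.5 and a gap of 30 points, the strata are 45% and 15%: (0.2475 + 0.1275)/2 = 0.1875 against 0.21. The variance falls by 11% and the half-width is 1.96 × √(0.1875/20) = 0.190.

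| Assumed gap | p = 0.30, f = 0.5 to 0.7 | p = 0.45, f = 0.5 to 0.7 |
|---|---|---|
| none (crude) | 0.201 | 0.218 |
| 10 points | 0.200 | 0.217 |
| 20 points | 0.196–0.197 | 0.214 |
| 30 points | 0.190–0.192 | 0.208–0.210 |

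With an 80/20 split and a 20-point gap at p = 0.30, the half-width is 0.198. These figures use true variances; step 5 deals with estimated ones.

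**3. Probability of correct selection** (simulated, two arms of 20, 45% against 30%, ties split).
- Exact balance: pooled and standardised selection are identical, 0.835 to 0.848 across gaps of 0 to 30 points.
- Counts off by up to one patient per arm: pooled 0.836–0.846, standardised 0.836–0.849.
- Arms differing by two patients, 30-point gap, equal strata: pooled 0.843, standardised 0.850.

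These figures average over imbalance in either direction. A particular imbalance matters more: a mix difference of k patients shifts the pooled comparison by gap × k/20. With k = 2 and a 30-point gap this is 0.03. The standard error of the difference is √((0.225 + 0.1875)/20) = 0.144, where 0.225 is the mean of 0.6 × 0.4 and 0.3 × 0.7. The selection probability is then about Φ(0.12/0.144) = 0.80 if the imbalance goes against the better schedule and Φ(0.18/0.144) = 0.89 if it favours it, against Φ(0.15/0.144) = 0.85 with balance.

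**4. Dependence on the enrolled mix.** Moving the untreated share from 50% to 80% with a 30-point gap moves the pooled rate by 0.30 × 0.30 = 0.09 in every arm. This leaves the ranking alone but changes what the reported rate describes.

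**5. Which interval.** Exact coverage of nominal 95% intervals with 10 + 10 patients and 30% survival overall:

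| Strata | Crude Wald | Plug-in stratified Wald |
|---|---|---|
| 40% / 20% | 95.3% | 92.5% |
| 45% / 15% | 96.0% | 91.8% |
| 50% / 10% | 96.8% | 91.1% |

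At 50%/10% there is a 35% chance that a stratum in an arm has no survivors or only survivors, so that its estimated variance is zero. Adding one success and one failure to each stratum before computing the interval restores about 95% to 96% coverage in the cases checked. Its half-width is 0.17–0.18, against about 0.195 on average for the crude Wald interval.

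**The case against.** The best defence is that stratified 1:1:1 allocation has already done the work. With balance kept, pooled rates compare fairly, selection is essentially unchanged, and the planned half-widths are the ones the crude analysis delivers. There is no test, and 11.1 says the trial is not powered to compare schedules. Larger gains need gaps near 30 points and evenly sized strata, and nothing in the documents supports those values. A naive stratified Wald interval would also be worse than the crude one.

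Most of this stands. It limits the size of the point and rules out the plug-in interval. Standardising can even cost a little: with no survival gap and allocation left to chance within arms, the simulated selection probability fell from 0.837 to 0.830 in the worst case (80/20 split).

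Two things are not answered. Section 5 leaves the randomization procedure to the Operations Manual, so the documents do not show how closely arms of 20 will balance. And balance between arms does nothing for a pooled AML rate that depends on the enrolled mix.

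A reader might also infer that the crude intervals are too narrow, that an error rate is inflated, or that the schedule choice is invalid. The documents support none of these: ignoring the factor makes the interval slightly too wide, 11.1.2 and 11.3.2 specify no test, and selection barely moves under balance. Nor are all strata ignored, since 11.4 keeps AML and MDS apart.

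**Conclusion.** The omission is real for both factors and its consequence is modest. At 30% survival, crediting the stratification would narrow the half-width from 0.201 to between 0.190 and 0.200 for assumed gaps of 30 down to 10 points. Correct selection changes by about 1 point or less on average, and more only if a particular imbalance arises.

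The case is strongest for Part 1 AML, where 11.1.3 itself expects shorter survival in relapsed patients. It would go too far to say that the protocol expects prior decitabine to affect survival: 11.3.3 speaks only of a possibly different response to the drug. All sizes rest on assumed gaps and shares. This is an inexpensive improvement, not a flaw that undermines the design.

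**What to change.** In 11.4:

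- Report 1-year survival by stratification factor within each arm, with numbers of patients.
- Pre-specify a stratum-standardised 1-year rate with the same weights in all arms, for estimation and for comparing schedules, and show it beside the crude rate. Do this for Part 1 AML first, then for prior decitabine in Parts 3 and 4.
- Use a small-sample stratified interval, for example with one success and one failure added per stratum, and not the plug-in Wald interval. The added counts serve the interval only; the point estimate stays unshrunk.
- If a stratum in an arm is empty, fall back to the crude rate, for all arms in that comparison.

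The cost is a little extra analysis work and no new data. The drawback is small strata, so rates by factor level will be imprecise and should be read as descriptive.

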#### 11.2. Sample Size for Part 2 of the Study

The Part 2 of the study is an open-label, single arm phase II study in elderly patients with previously untreated AML and significant concomitant medical illnesses as measured by having HCTCI of 2 and higher. There are two co-primary efficacy endpoints, the rate of clinical benefit response (CR, CRp, PR, major HI or SD) and the rate of complete response (CR or CRp). Secondary endpoints are response duration, transfusion requirements, number of hospitalized days, overall survival, and safety. Statistically, the purpose of the trial is to reject sapacitabine from further study in elderly AML patients with HCTCI of 2 and higher if it were insufficiently active, and to accept it as active if it were truly active.

The trial is based on the following assumptions:

- The inactivity cut-off is chosen equal to 5% clinical benefit response; the activity cut-off is equal to 30% clinical response rate; hence, the hypotheses of interest are  $H_0$ :  $r \le 5\%$  against  $H_A$ :  $r \ge 30\%$ , where r is the response rate.
- The type I error rate ( $\alpha$ , probability of accepting an insufficiently active treatment, a false positive outcome) is set to 5%.
- The type II error rate ( $\beta$ , probability of rejecting an active treatment, a false negative outcome) is set to 5%.

Under these assumptions, a two-stage design uses the following decision rule:

After treating up to 12 evaluable patients defined as those who have completed at least one treatment cycle,

- If no response is observed, declare the treatment insufficiently active and no more patient will be treated with this dose regimen
- If at least one response is observed, add patients to reach a maximum of 24 patients and
  - o If three responses or less are observed, declare the treatment insufficiently active
  - o If at least four responses are observed (an observed response rate of at least 17%), declare the treatment sufficiently active and add patients to reach a maximum of 36 patients.

The dose regimen will be considered active if the clinical benefit rate is at least 30% or the

rate of CR/CRp is at least 20%. Since the trial has two co-primary endpoints, the 97.5% confidence interval is calculated for each of the two endpoints. Assuming that the true response rate is equal to 30% clinical benefit rate and 20% CR/CRp, 36 patients are required for the lower bound the of the 97.5% confidence interval to exclude 5% for both endpoints.

#### 11.3. Sample Size for Part 3 and 4

The primary objective of Part 3 and 4 of the study is to evaluate 1-year survival rate of 3 dosing schedules in elderly patients with previously untreated AML which evolved from MDS after receiving hypomethylating agents for the MDS or older patients with previously treated MDS; the secondary objectives are to assess the number of patients who have achieved a CR, CRp, PR, major HI or SD and their corresponding durations, transfusion requirements, number of hospitalized days and safety.

The primary efficacy endpoint is 1-year survival measured from the date of randomization. Statistically, the purpose of the trial is to reject the dosing schedules from further study if they were insufficiently active based on the rate of clinical benefit response and to accept them for further study if they were truly active. For "screening" purpose, a Bayesian continuous futility monitoring rule is used for each dose schedule separately based on the rate of clinical benefit response, and a "selection" design to choose the better dosing schedule based on 1-year survival rate if all 3 dosing schedules are found to have activity based on the rate of clinical benefit response. This randomized phase II trial is not expected to have sufficient power to compare the 3 dosing regimens on the basis of 1-year survival rate.

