#### 11.1.1. Screening Design

In the screening phase, a Bayesian continuous futility monitoring rule will be implemented based on the rate of CR plus CRi in each of the 3 arms of the AML stratum, respectively. An arm will be stopped if Prob (CR+CRi > 25% | data) < 0.05. The above stopping rule suggests that, given the data obtained from patients who have already been evaluated in an arm, if there is less than a 5% chance that the rate of CR+CRi is greater than 25% we will terminate the arm. This decision rule generates the following stopping boundaries, assuming a beta(1,1) prior distribution for the response (CR+CRi) rate in each arm. Stop an arm i if [ # of pts with CR or CRi in arm i / # of pts evaluated in arm i ]  $\leq$  0/10, 1/17, where i = 1, 2, or 3. The operating characteristics of this rule are shown in Table 8.

Table 8 Operating Characteristics of Futility Monitoring - Maximum 20 AML Patients

		Sample Size		
Rate of CR or CRi	Probability of stopping	P 25	P 50	P 75
0.05	0.822	10	10	17
0.10	0.54	10	17	20
0.15	0.313	17	20	20
0.20	0.165	20	20	20
0.25	0.082	20	20	20
0.30	0.039	20	20	20

After treating up to 10 evaluable AML patients defined as patients who have completed at least 1 cycle of treatment at each dosing schedule

- If no CR or CRi is observed, declare the treatment insufficiently active and no more AML patient will be treated with this dose regimen
- If at least one CR or CRi is observed, add AML patients to reach a total of 17 patients and
  - o If less than two CR plus CRi are observed, declare the treatment insufficiently active
  - o If at least two CR and CRi are observed, add AML patients to reach a maximum of 20 patients

For both AML and MDS patients, there is an early stopping rule for excessive toxicity. A dosing schedule will be declared to have excessive toxicity and no more patients will be treated with this dose regimen if among the first 10 patients treated with this dose regiment in either the AML or MDS stratum, there are > 2 patients experienced serious adverse events (excluding simple complications associated with myelosuppression such as neutropenic fever without shock or its complications from gram-negative bacteremia, anemia or mucosal bleeding, *e.g.*, epistaxis, due to thrombocytopenia easily controlled by transfusion) that are considered by investigator to be definitely, probably or possibly related to the study drug during the first two treatment cycles.

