  - o If at least two CR, CRp, PR, major HI or SD are observed in Part 3, add AML patients to reach a maximum of 20 patients; if least two CR, CRp, PR, major HI or SD are observed in Part 4, add MDS patients to reach a maximum of 20 patients

There is an early stopping rule for excessive toxicity. A dosing schedule will be declared to have excessive toxicity and no more patients will be treated with this dose regimen if among the first 10 patients treated with this dose regiment, there are > 2 patients experienced serious adverse events (excluding simple complications associated with myelosuppression such as neutropenic fever without shock or its complications from gram-negative bacteremia, anemia or mucosal bleeding, *e.g.*, epistaxis, due to thrombocytopenia easily controlled by transfusion) that are considered by investigator to be definitely, probably or possibly related to the study drug during the first two treatment cycles.

If a dosing schedule has at least 4 CR, CRp, PR, major HI, or SD, and the 30-day death rate is 20% or less, additional AML or MDS patients may be added to confirm the safety and tolerability of that dosing schedule.

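### Part 2, the only part that selects patients for comorbidity, has neither the excessive-toxicity stopping rule nor the 30-day death condition that the protocol sets for every other part.

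*Combined protocol and SAP*

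**What the plan says.** **Parts 1, 3 and 4.** Section 11.1.1 (Part 1) states: "For both AML and MDS patients, there is an early stopping rule for excessive toxicity". Section 11.3.1 (Parts 3 and 4) repeats it: "There is an early stopping rule for excessive toxicity". In both, a schedule takes no more patients if "among the first 10 patients treated with this dose regiment, there are > 2 patients experienced serious adverse events" that the investigator judges at least possibly related to the drug, within the first two cycles. Simple complications of myelosuppression are excluded. Both sections also set a condition for adding patients to a schedule that has shown activity: at least 4 responders and a 30-day death rate of 20% or less.

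**Part 2.** Section 11.2 defines the population by "significant concomitant medical illnesses as measured by having HCTCI of 2 and higher". It has three decision points, all based on response:
- At 12 patients: "If no response is observed, declare the treatment insufficiently active and no more patient will be treated with this dose regimen".
- At 24: three or fewer responses means insufficiently active.
- At 24 with four or more responses: "declare the treatment sufficiently active and add patients to reach a maximum of 36 patients".

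No toxicity count or death rate enters any of these.

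**Whole trial.** Section 3.5 allows discontinuation for safety concerns, without a threshold, a number of patients or a time. Section 11.4 reports 14-day and 30-day mortality with confidence intervals, but attaches no action to them.

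**The concern.** Section 4.1.1 makes an HCTCI of 2 or higher an entry criterion for Part 2 and for no other part. One would expect a cohort chosen for concomitant illness to have at least the cohort-level safety checks that the other parts have. It has fewer.

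The design does not obviously explain the gap. Part 3 Arm F starts on the same schedule as Part 2 and is covered by the rule. The rule works within one schedule and needs no comparator, so a single-arm part could use it. Less myelosuppression on this schedule is, in Section 3.3, a hypothesis that Part 2 is meant to test. No reason for the difference is given.

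At stake is whether a high rate of serious toxicity would stop accrual by a prespecified rule, or only if someone chose to act under Section 3.5.

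**Working it through.** **Step 1. Does the Part 1 rule reach Part 2?** Its reference to AML and MDS patients is to the two strata, and the rule counts patients within either stratum. Section 3.1 defines those strata for Part 1 only. The rule in Section 11.3.1 stands under the heading for Parts 3 and 4. Neither covers Part 2.

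**Step 2. Reproduce the Part 2 design.** From Section 11.2: at least 1 response in the first 12, at least 4 in 24, and "The inactivity cut-off is chosen equal to 5% clinical benefit response; the activity cut-off is equal to 30% clinical response rate"; type I and type II error are each set at 5%. With p the true response rate, taken here as clinical benefit,

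P(go on to 36) = P(X ≥ 4; n = 24) − P(0 of first 12) × P(Y ≥ 4; n = 12),

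where X and Y are binomial with rate p. The second term removes paths that meet the total but would have stopped at 12.

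| p | P(X ≥ 4 of 24) | P(0 of 12) = (1−p)^12 | P(Y ≥ 4 of 12) | P(go on to 36) |
|---|---|---|---|---|
| 0.05 | 0.0298 | 0.5404 | 0.0022 | 0.0286 |
| 0.20 | 0.7361 | 0.0687 | 0.2054 | 0.7220 |
| 0.30 | 0.9576 | 0.0138 | 0.5075 | 0.9506 |

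Type I error is 0.029 and type II error is 1 − 0.9506 = 0.049, so both stated limits are met. The 36 also reproduces. The Wald lower bound of a 97.5% interval at a 20% rate is 0.20 − 2.2414 × √(0.16/36) = 0.0506, which excludes 5%; at 35 patients it is 0.0485. At a 30% rate and 36 patients it is 0.129. The efficacy design is sound on its own terms, and no toxicity quantity enters it.

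**Step 3. What the Part 2 text does when toxicity is high.** The prespecified probability of a toxicity stop is 0 at every SAE rate. The probability of going on to 36 stays at 0.72 (20% benefit) or 0.95 (30% benefit).

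**Step 4. What the other parts' rule would do.** With t the true rate of qualifying SAEs, P(stop) = P(3 or more of 10) = 1 − P(0) − P(1) − P(2). At t = 0.30 this is 1 − 0.0282 − 0.1211 − 0.2335 = 0.617. The documents give no t for Part 2, so a range is assumed. The last column is 0.9506 × (1 − P(stop)), with toxicity and response taken as independent.

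| Assumed t | P(stop) | P(go on to 36) at 30% benefit, with the rule |
|---|---|---|
| 0.10 | 0.070 | 0.88 |
| 0.20 | 0.322 | 0.64 |
| 0.30 | 0.617 | 0.36 |
| 0.40 | 0.833 | 0.16 |

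The effect of the 30-day death condition is not computed, because the documents give no Part 2 death rate.

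**The case against.** The best case for the text is that the parts may differ by design. Part 2 starts below the Arm C dose in the expectation of less myelosuppression. Arm F shares its starting schedule but enrols a different population under randomization. Section 3.5 permits a safety stop, and the dose-reduction provisions of Section 6.2, including those for frail patients, name Part 2. The 30-day death condition governs optional additions to a schedule in the other parts, whereas 36 is the planned Part 2 size.

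Much of this stands. A difference between parts is not in itself a contradiction, and accrual on efficacy alone describes the prespecified rules, not everything that the sponsor may do. But none of these provisions sets a cohort-level boundary, and no reason for omitting one is stated.

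A reader might infer more than the documents support:
- **That Part 2 has the most comorbid patients.** It is the only part selected on HCTCI. The other parts neither require nor cap the score, and the ECOG, renal, hepatic and intercurrent-illness criteria apply to all parts.
- **That accrual to 36 is nearly certain.** The probability of passing the first look is 0.93 at a 20% benefit rate and 0.99 at 30%, but the second look at 24 lowers the probability of going on to 36 to 0.72 and 0.95.
- **That Part 2 alone leaves out patients who fail to finish cycle 1.** Section 11.2 does look "After treating up to 12 evaluable patients defined as those who have completed at least one treatment cycle", but the response looks in the other parts use the same definition. The toxicity rule elsewhere already counts patients treated.

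**Conclusion.** The gap is real. Part 2 is the only part selected for comorbidity and the only one with no excessive-toxicity rule, and its expansion from 24 to 36 carries no 30-day death condition. Its formal path to 36 does not respond to toxicity: the probability is 0.72 at a 20% benefit rate and 0.95 at 30%. The rule used elsewhere would stop accrual with probability 0.07 to 0.83 over SAE rates of 10% to 40%.

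The gap itself rests on the text alone. Its size rests on assumed SAE and benefit rates, on all 12 and 24 patients being evaluable, and, where the two rules are combined, on independence of toxicity and response. The efficacy error rates are not in question. This should be settled in the protocol, but it does not show that Part 2 is unsafe or that no one could stop it.

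**What to change.** Reconcile Section 11.2 with Sections 11.1.1 and 11.3.1. Either state that Part 2 comes under the protocol's own cohort-level safety conditions (the excessive-toxicity rule, and the 30-day death condition at the expansion from 24 to 36), or state why it is exempt. The choice is for the sponsor and its clinical advisers. Both conditions need attention: the toxicity rule looks only at the first 10 patients, so by itself it would not bear on the later expansion.

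The drafting cost is about a paragraph, with no new data. If Part 2 is covered by the toxicity rule, the chance of stopping is 7% at a true SAE rate of 10% and 32% at 20%. The chance of going on to 36 at a 30% benefit rate then falls from 0.95 to about 0.88 and 0.64. The stated 5% type II error would no longer describe the chance of completing Part 2, and Section 11.2 should say so. The other parts already accept the same rule.
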